Statistical Analysis Plan

Uterotonic prophylaxis after D&E

PI: [name]
University of California, San Francisco

Statistical Analysis Plan

We plan to use t-tests for continuous variables and a chi-square analysis for categorical variables for comparison of study groups at baseline. In the event that the groups are not comparable at baseline, we will do a multivariable analysis adjusting for possible confounders. We will do an intent-to-treat analysis as our primary analysis. If a woman is noted to have elevated blood pressure ($>140/90$) at the completion of the D&E, the study drug will be withheld as this would be a contraindication for MM. These women will still be analyzed in their original randomization group to ensure fidelity to randomization's goal of balancing confounders. In addition to computing the dichotomous outcome of blood loss $> 125\text{cc}$ and/or intervention for bleeding, we will also compare the number of interventions listed in Table 1 for each group. We will also do a sensitivity analysis of the composite outcome in which we exclude the more minor interventions for bleeding, use of uterotonic or manual pressure. For our secondary outcome of mean blood loss difference, we will also conduct a per-protocol analysis, comparing those who received any uterotonic medication (placebo plus additional doses as well as intervention arm plus or minus additional doses) versus those who received no uterotonic.

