STUDY PROTOCOL
Uterotonic prophylaxis after D&E

PI: [name]
University of California, San Francisco

STUDY PROTOCOL

Study Design

We propose a three-arm randomized, double-blinded, placebo-controlled trial of intramuscular MM versus rectal misoprostol versus placebo after D&E to evaluate the effect of prophylaxis on excessive bleeding. All English- or Spanish- speaking women undergoing D&E at San Francisco General Hospital's Women's Options Center (SFGH WOC) between 20 weeks' 0 days' and 24 weeks' 0 days' gestation will be eligible for recruitment. Women will be excluded if they have a pre-operative diagnosis of hypertension, are using protease inhibitors, have known coagulopathy or history of obstetric hemorrhage requiring blood transfusion, placenta accreta, increta or percreta, and any other contraindication to MM or misoprostol use.

Study Procedures

Recruitment: All eligible women will be identified on the pre-operative day by the research assistant, after clinical staff performs an ultrasound to determine the gestational age. For most women, the pre-operative day is one day prior to the D&E. For a minority of women, it is two days prior to the D&E. After eligibility is confirmed, the research assistant will approach the patient prior to dilator placement to explain the study, and obtain consent.

Randomization: On the day of the D&E, women who consented to participate in the trial will be assigned a study number and random assignment to one of three study arms will be made. We plan to use block randomization for two gestational age ranges (1) 20 weeks 0 days to 22 weeks 0 days; (2) 22 weeks 1 day to 24 weeks 0 days. We plan to use a random number table to assign each study number to one of three arms. By randomizing women just prior to the D&E, we will minimize any negative effect on the randomization scheme if women either fail to return for the procedure or withdraw consent prior to the D&E.

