Primary outcome: Our primary outcome of excessive bleeding will be measured with a composite outcome that includes measured post-operative blood loss greater than 125 cc or specific interventions done to manage the excessive bleeding (Table 1). Only one of the listed criteria is needed to qualify as a positive outcome. In addition to our primary, composite outcome, we will also record the number of interventions performed for what the provider deems excessive uterine bleeding. We plan to do sensitivity analyses as follows: (1) a dichotomous outcome of 2 or more interventions used versus less than 2; (2) excluding administration of uterotronics and uterine pressure.

We are not aware of any literature measuring blood loss after D&E at 20 to 24 weeks' gestation. In our clinic, we have observed that approximately 95% of women within this gestational age range have a total post-operative blood loss to be less than 125 cc. We are thus considering greater than 125 cc post-operative blood loss to be indicative of excessive bleeding, and thus have included it as one of the criteria for our composite outcome. For uterotonic medications administered or prescribed, we will record the type (misoprostol, hemabate, MM), dosage, and number of doses.

Many cases of excessive bleeding will fulfill more than one criterion listed in Table 1. For example, most women given a prescription for a uterotonic medication at discharge will likely have received a uterotonic medication. In addition, most women with > 125 cc blood loss post-operatively will likely have received at least one uterotonic medication. In order to increase our sensitivity in detecting excessive bleeding, we have included all possible criteria, and will record the number of interventions someone received. Providers who wish to give a uterotonic medication to treat excessive bleeding will be instructed to wait 5 min after the study drug has been given. They will be able to choose any uterotonic as they normally would.

Table 1. Clinical factors included in composite outcome of excessive bleeding after D&E.

Total blood loss > 125 cc (after D&E)	
Secondary outcome: A secondary outcome will be overall blood loss after the D&E. Blood loss will be measured from the start of the procedure, defined as removal of cervical dilators, to the end of the procedure (after last suction). All bleeding that occurs after last suction will be

Transfusion	
Admission for bleeding	
Re-aspiration for bleeding	

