Balloon tamponade	
Uterine artery embolization	
Major surgery for bleeding	
At least 1 uterotonic medication given	
Prescription given for any uterotonic medication at discharge	
Uterine compression (uterine massage or manual pressure for 2 minutes	

considered post-operative bleeding. Blood loss will be measured by collecting the blood in a draped bag underneath the patient and by weighing all gauze used during the procedure. To assess post-procedure blood loss in the recovery room, we will also weigh pads and chux from the time of last suction to discharge, then converting grams into milliliters using the specific gravity of blood which is 1.06 grams per milliliter (Figure 1). We will compare mean total blood loss volume (TBLV) after D&E, a continuous outcome, among the three arms. We have successfully piloted this method of measuring blood loss in our clinic.

Figure 1. Measuring total blood loss after D&E

TPW (grams)	Total pad weight = weight of all pads used
TBLW (grams)	Total blood loss weight = Total pad weight – (Dry pad weight * # of pads)
TBLV (milliliters)	Total blood loss volume = Total blood loss weight / 1.06 g/mL

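### Randomisation is blocked within two gestational-age ranges, but nothing in the SAP ensures that this factor enters the analysis; a stratified primary analysis is a small improvement at no cost.

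*SAP*

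**What the plan says.** **Design.** The protocol, under Randomization, states: "We plan to use block randomization for two gestational age ranges". The ranges are 20 weeks 0 days to 22 weeks 0 days, and 22 weeks 1 day to 24 weeks 0 days. No block size is given, and the same paragraph adds: "We plan to use a random number table to assign each study number to one of three arms".

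**Primary analysis.** The SAP states: "We will do an intent-to-treat analysis as our primary analysis". That fixes the analysis set. The SAP then says the dichotomous composite will be computed, but gives no test, model, effect measure, contrast or stratum term for it.

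**Secondary outcome.** The protocol states: "We will compare mean total blood loss volume (TBLV) after D&E, a continuous outcome, among the three arms". Neither document names a test or a stratum term for this comparison.

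**Tests that are named.** These are tied to baseline: "We plan to use t-tests for continuous variables and a chi-square analysis for categorical variables for comparison of study groups at baseline".

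**Adjustment.** It is conditional: "In the event that the groups are not comparable at baseline, we will do a multivariable analysis adjusting for possible confounders". There is no threshold, covariate list or model, and no statement of whether the adjusted result replaces or supplements the unadjusted one.

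**The concern.** Gestational age is the one factor that the designers chose to control at randomisation, and the analysis does not mention it. Blocking within ranges gains precision only if the analysis then uses the ranges. If it does not, the standard error still contains between-range variation that the design has removed from the treatment comparison.

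The conditional rule does not close the gap. Blocking keeps the arms balanced on the range, so a baseline test of the range itself would not be expected to set the rule off. An imbalance in some other variable could bring gestational age in as a possible confounder, but that would depend on chance and on judgement. The SAP elsewhere appeals to randomisation's "goal of balancing confounders", which sits uneasily with a rule that makes adjustment depend on a baseline check.

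At stake are a modest amount of power and an unspecified choice of analysis.

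**Working it through.** **Inputs.** The documents state no sample size, alpha, power, composite event rate or rate by range, so there is no figure of the plan's to reproduce. The only rate given is for one component, in the protocol under Primary outcome: "approximately 95% of women within this gestational age range have a total post-operative blood loss to be less than 125 cc", or roughly 5% above that limit. Everything else here is assumed: a two-sided 5% test of one arm against another, planned at 80% power, with equal-sized ranges exactly balanced by blocking.

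**Step 1: within-range share of the variance.** For event rates p1 and p2 in the two ranges, with mean p:

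r = {[p1(1−p1) + p2(1−p2)] / 2} / [p(1−p)]

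- 25/35%: (0.1875 + 0.2275)/2 = 0.2075; 0.2075/0.21 = 0.988
- 20/40%: (0.16 + 0.24)/2 = 0.20; 0.20/0.21 = 0.952
- 2.5/7.5%: 0.0469/0.0475 = 0.987
- 1.67/8.33%: 0.0464/0.0475 = 0.977

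**Step 2: cost of an unstratified test.** The unstratified test uses a standard error too large by the factor 1/√r, so its effective critical value is c = 1.96/√r. Then:

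- type I error = 2[1 − Φ(c)]
- power = 1 − Φ(c − 2.80)
- effective sample loss = 1 − [(1.96 + 0.84)/(c + 0.84)]²

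For 20/40%: c = 1.96/√0.952 = 2.008, and the loss is 1 − (2.80/2.85)² = 3.4% when unrounded values are carried through.

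| Rates in the two ranges | r | Type I error | Power | Effective sample loss |
|---|---|---|---|---|
| 30/30% | 1.000 | 5.00% | 80.0% | 0 |
| 25/35% | 0.988 | 4.86% | 79.7% | 0.8% |
| 20/40% | 0.952 | 4.46% | 78.6% | 3.4% |
| 2.5/7.5% | 0.987 | 4.85% | 79.6% | 0.9% |
| 1.67/8.33% | 0.977 | 4.73% | 79.3% | 1.6% |

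Losses of 8% and 14% need contrasts of 15/45% and 10/50%, which nothing in the documents suggests.

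**Step 3: if balance within ranges is not achieved.** Block size is not stated, so exact balance is an assumption. With unrestricted allocation the unstratified test holds 5% error and loses 1 − r: 1.2% at 25/35%, 4.8% at 20/40%. The case for stratifying holds either way.

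**Step 4: would a baseline test pick up the range?** Assume 50 women per arm in each range from complete blocks, plus one incomplete block in each range. With blocks of 12, the most extreme split gives p = 0.81 in a single three-arm chi-square test. For a pair of arms split 54/50 and 50/54, the difference is 54/104 − 50/104 = 0.0385 with standard error √(0.25 × 2/104) = 0.0693, so z = 0.55 and p = 0.58. These values depend on the assumed layout and are not lower bounds, but both are far from 0.05.

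**Step 5: what stratifying costs if the range does not matter.** In simulation (30% risk in both ranges, odds ratio 0.4, 200,000 runs), the unstratified test and the Cochran-Mantel-Haenszel test had power of 75.3% and 75.0% at 100 per arm, and 53.8% and 52.9% at 60 per arm. In the latter case the unstratified test ran at 5.3% error against 5.0%, which accounts for part of the difference.

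**The case against.** **The rule could bring gestational age in.** The SAP's phrase about possible confounders is not limited to the variables found imbalanced. Gestational age could also be compared as a continuous variable, which two-range blocking does not balance within a range. This stands: a reader might infer that the rule shuts the randomisation factor out, and the text does not support that. It supports only that inclusion is left unspecified.

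**The harm is small and undocumented.** This stands too. A reader might infer bias or an inflated false-positive rate from the missing stratum term. Neither follows: the unstratified intent-to-treat comparison is valid and, with blocked strata, slightly conservative. Every power figure rests on assumed rates.

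**The conditional rule does not by itself inflate error.** Applied mechanically it kept error at 4.4 to 5.0% in simulation. An excess, to about 5.4 to 6.5%, appears only if its firing leaves a free choice of which result to report, and also needs an assumed p<0.05 criterion, 10 baseline variables and an assumed prognostic strength (5 to 20% of variance). The SAP does not say that such a choice will be made, so that excess should not be charged to it.

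**Chi-square may be the intended outcome test.** Possible, but the sentence ties it to baseline. If it was meant, it would still be unstratified.

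**Conclusion.** The point holds as a minor improvement that costs nothing. The design is blocked on gestational age, the SAP fixes no outcome test or stratum term, and the one conditional adjustment does not guarantee that the factor is used. Nothing elsewhere in either document supplies it.

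Under the assumed rates and blocked, equal-sized ranges, the loss is about 1 to 3% of effective sample for contrasts of 25/35% to 20/40%, and 1 to 2% at a 5% mean rate. The true figure is unknown, because the documents give neither the composite rate nor any rate by range. The case rests on a gap that can be closed without cost. It does not rest on a demonstrated threat to the trial's conclusion.

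**What to change.** Amend the SAP as follows.

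1. Make the primary intent-to-treat analysis of the composite a Cochran-Mantel-Haenszel test stratified by the two randomisation ranges.
2. State whether this is one three-arm test on 2 degrees of freedom or named pairwise contrasts (each active arm against placebo), and the alpha used. With three arms, a stratified test is not fully defined without this.
3. Report the Mantel-Haenszel risk difference with its 95% confidence interval for each named pair.
4. Analyse blood loss volume with a linear model containing arm and stratum.
5. Replace the baseline-comparability rule: any further covariate-adjusted model is supplementary, with its covariates named before unblinding.

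**Cost.** SAP wording only. The range is known at randomisation, and no patients or data are added. If the ranges turn out not to be prognostic, power is essentially unchanged: lower by at most about 0.3 points at 100 per arm and 0.9 at 60 per arm in the simulations above.

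### The SAP's per-protocol analysis of mean blood loss groups women by uterotonic received, so the groups depend on bleeding and the result is generally biased against the drugs

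*SAP*

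**What the plan says.** The Statistical Analysis Plan makes intent-to-treat primary. Of women whose study drug is withheld for raised blood pressure it says: "These women will still be analyzed in their original randomization group to ensure fidelity to randomization's goal of balancing confounders". For the secondary outcome of mean blood loss it then adds an analysis that it calls per-protocol, "comparing those who received any uterotonic medication (placebo plus additional doses as well as intervention arm plus or minus additional doses"). The other side of the contrast is given as "versus those who received no uterotonic".

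The Protocol (Outcomes) explains how the extra doses arise and what is measured:

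- Reason for rescue: "Providers who wish to give a uterotonic medication to treat excessive bleeding will be instructed to wait 5 min" after the study drug.
- Expected link to bleeding: "most women with > 125 cc blood loss post-operatively will likely have received at least one uterotonic medication".
- Measurement window: "we will also weigh pads and chux from the time of last suction to discharge".
- Main analysis of this outcome: "We will compare mean total blood loss volume (TBLV) after D&E, a continuous outcome, among the three arms".

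Table 1 of the Protocol also counts a single uterotonic dose as an excessive-bleeding event.

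**The concern.** A per-protocol analysis normally keeps women in their randomised arm and restricts to those who adhered. This one discards the arms. A placebo woman who bleeds and is rescued joins the treated group, and a placebo woman who does not need rescue stays in the comparator. The only others in the comparator are women whose study drug was withheld and who needed no rescue.

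Group membership is therefore partly a consequence of the outcome being compared. Adjusting for baseline covariates, the only adjustment the SAP foresees, does not remove selection on the outcome itself, and the SAP states no caveat. Methylergonovine (MM) and misoprostol are also merged, so the contrast estimates neither drug's effect.

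Readers would take a result labelled per-protocol as supporting or challenging the randomised comparison. A working drug could look weak or harmful.

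**Working it through.** **Inputs.** The documents give no rescue rate, mean, SD, effect size, sample size or alpha, so there is no plan figure to reproduce. Their one quantitative anchor is that about 95% of the clinic's women in this gestational range lose less than 125 cc post-operatively. The allocation ratio is not stated; 1:1:1 is assumed.

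**Exact result, no drug withheld.** Let *r* be the share of placebo women rescued, *D* the mean measured loss of rescued minus non-rescued placebo women, *δ* the true mean reduction in the active arms, and *m₀* the mean of non-rescued placebo women.

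- Placebo mean = *m₀* + *rD*; active mean = *m₀* + *rD* − *δ*
- Any-uterotonic mean = [2(*m₀* + *rD* − *δ*) + *r*(*m₀* + *D*)] / (2 + *r*)
- No-uterotonic mean = *m₀*
- SAP contrast = (3*rD* − 2*δ*) / (2 + *r*), where the randomised contrast is −*δ*
- Bias = *r*(3*D* + *δ*) / (2 + *r*)

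The bias is against the drug whenever *D* > −*δ*/3, hence in every case where rescued women bled more. Even at *D* = 0 the effect is diluted to −2*δ*/(2 + *r*). The sign reverses when *D* > 2*δ*/(3*r*): 13.3*δ* at 5% rescue, 4.4*δ* at 15%, 2.2*δ* at 30% and 1.3*δ* at 50%.

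**Size under assumptions.** Placebo loss is taken as lognormal with its 95th percentile at 125 mL before any rescue effect. Its mean is 125·exp(−1.645σ + σ²/2), where σ is the log-SD: 46.2 mL at σ = 0.8, so a 20% reduction is 9.2 mL. The grid has σ of 0.6, 0.8 and 1.0; rescue in 5, 15, 30 and 50%; and correlation of 0.3 or 0.6 between rescue propensity and log loss. That is 24 scenarios for each level of rescue benefit, all with a true 20% reduction. The last column is σ = 0.8, 30% rescued, correlation 0.6.

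| Rescue cuts total loss by | Intent-to-treat (mL) | SAP contrast (mL) | Sign reversed | Example (mL) |
|---|---|---|---|---|
| 0% | −8 to −11 | −9 to +15 | 12 of 24 | −9.2 becomes +7.6 |
| 15% | −7 to −11 | −10 to +11 | 8 of 24 | −8.2 becomes +4.2 |
| 30% | −6 to −11 | −10 to +6.5 | 4 of 24, one more at zero | −7.2 becomes +0.7 |

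Of these 72 scenarios, 71 shift against the drug. None of the 18 at 5% rescue reverses; for example, −9.2 becomes −3.9 mL (σ = 0.8, correlation 0.6, no rescue benefit).

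**Separate check with σ = 0.7** (mean about 50 mL, no rescue benefit, correlation 0.6). At *r* = 0.30, *D* = 38.3 and *δ* = 10.0: (3 × 0.30 × 38.3 − 2 × 10.0) / 2.30 = +6.3 mL. At *r* = 0.05, *D* = 64.3 and *δ* = 10.1: (3 × 0.05 × 64.3 − 2 × 10.1) / 2.05 = −5.2 mL.

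**Drug withheld.** With 5–10% withheld, a 10% rescue effect, 30% rescue and correlation 0.6, intent-to-treat is −8.9 to −8.4 mL and the SAP contrast +4.3 to +4.9 mL.

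**No true effect of drug or rescue** (σ = 0.7, correlation 0.6, two-sided 0.05 t-test, assumed total N of 100, 150 and 300). The any-versus-none test rejects 28%, 38% and 60% of the time at 15% rescue, and 54%, 72% and 93% at 30% rescue. Intent-to-treat stays at 4–6%.

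**The case against.** The strongest objection concerns direction. *D* is measured after rescue, so its sign depends on how well rescue works, which the documents do not say. If rescue halves total loss, only 9 of the 24 scenarios shift against the drug and one reverses; the other 15 tie or shift towards it. With σ = 0.6, 30% rescue and correlation 0.3, for example, intent-to-treat is about −8 mL and the SAP contrast −13.6 mL. This stands as a limit: the direction is not universal. However, in each of these counterexamples fewer than half of the women with measured loss above 125 mL were rescued, whereas the Protocol expects most of them to have received a uterotonic. Every scenario run that meets that expectation shifts against the drug. This uses measured total loss, as the Protocol phrases it; judged on loss before any rescue effect, some counterexamples would qualify.

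Second, reversal is not the typical result. It occurs in 24 of the 72 scenarios, and grid counts are not probabilities. The example column uses the higher correlation; at 0.3 with no rescue benefit, the same case falls just below zero. This also stands.

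Third, this is an additional analysis of a secondary outcome, and the SAP discloses the composition of the groups in the same sentence. That limits the harm, but disclosure does not make the contrast valid or the label right.

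**Conclusion.** The concern holds. As written, the analysis is an as-treated comparison whose groups depend on the outcome. It is biased against the drugs whenever rescued placebo women bled more than those not rescued, which is what the Protocol's own text leads one to expect. Attenuation is the usual result when rescue is rare; reversal needs rescue to be both common and strongly linked to bleeding. A very effective rescue could push the bias the other way.

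The algebra is exact under equal allocation with no drug withheld. The millilitre figures rest on an assumed distribution, rescue rate, correlation and effect size, and are not predictions for this trial. The damage is confined to a misleading supplementary result, so this should be fixed but does not threaten the main conclusions.

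**What to change.** Replace the any-versus-none contrast in the SAP with wording such as:

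> The per-protocol analysis of blood loss will include women who received both their assigned injection and their assigned tablets, analysed in their randomised arm. MM will be compared with placebo, misoprostol with placebo, and MM with misoprostol. Later uterotonic treatment will not change a woman's group.

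The decision to withhold study drug is made before dosing and under blinding. If the blind holds, leaving those women out of this analysis should not favour an arm.

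Tabulate rescue uterotonic use by arm as an outcome in its own right. The data are already planned: "For uterotonic medications administered or prescribed, we will record the type (misoprostol, hemabate, MM), dosage, and number of doses". The SAP's planned count of Table 1 interventions does not show uterotonics separately.

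The minimum alternative is to drop the exposure contrast, or to keep it labelled as exploratory and as-treated. The label should carry a note that rescue follows bleeding, that the bias is expected to run against the drugs, and that it could run the other way if rescue is very effective.

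The cost is SAP wording and a little analysis work. No new data are needed and nothing in patient management changes.
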